#### **10.6.3.3 Laboratory Abnormalities**

For laboratory tests covered by the Common Terminology Criteria for Adverse Events (CTCAE) version 4.0, the study's biostatistical and reporting team will grade laboratory data accordingly.

For laboratory tests covered by CTCAE, a grade 0 will be assigned for all non-missing values not graded as 1 or higher. Grade 5 will not be used.

In some cases (e.g. white blood cell differentials), the lower limits of normal ranges used in CTCAE definition may have to be replaced by a clinical meaningful limit expressed in absolute counts.

For laboratory tests where grades are not defined by CTCAE, results will be graded by the low/normal/high classifications based on laboratory normal ranges.

The following summaries will be generated separately for hematology, biochemistry and urinary laboratory tests:

- frequency table for newly occurring on-treatment grades 1, 2, 3 or 4 (see below for details)
- shift tables using CTCAE grades to compare baseline to the worst on-treatment value
- for laboratory tests where CTCAE grades are not defined, shift tables using the low/normal/high/(low and high) classification to compare baseline to the worst on-treatment value.
- listing of all laboratory data with values flagged to show the corresponding CTCAE grades and the classifications relative to the laboratory normal ranges.

In addition to the above mentioned tables and listings, other exploratory analyses, for example figures plotting time course of raw or change in laboratory tests over time or box plots will be generated when appropriate.

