## **Other reported toxicities**

Increased gamma glutamyltransferase and hypokalemia were the other laboratory DLTs, whereas fatigue/asthenia were the other non-laboratory DLTs reported in. For both dosing schedules (once daily and 5 days on/2 days off), fatigue/asthenia were listed among the commonly reported AEs ( $\geq 10\%$  of patients). In addition, fatigue/asthenia had high incidences among all grade 3/4 events.

Other commonly reported adverse events from both dosing schedules, regardless of study drug relationship, include headache, dyspnea, constipation, pyrexia, cough, dyspepsia, and dry mouth. About 3.9% of patients (n = 16) reported for palmar-plantar erythrodysesthesia syndrome (PPES) in the studies using 5 days on/2 days off dosing schedule (N = 378 global studies, and N = 28 Japan study 1101). Among them, 3 grade 3 events were reported and no grade 4 events were observed. PPES has also been reported with the use of other tyrosine kinase inhibitors.

Serum amylase and triglycerides are monitored in the clinical studies with dovitinib, because their abnormal levels were reported in the preclinical toxicology studies. Newly occurring or worsening grade 3/4 increase in triglycerides were reported in patients who have received dovitinib treatment in clinical trials of the 5 days on/2 days off dosing schedule; 88 with grade 3 and 18 with grade 4.

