## 7 Visit schedule and assessments

### 7.1 Study Flow and Visit Schedule

[Table 7-1](#) lists all of the assessments except for laboratory assessments and indicates with an “X” the visits when they are performed. [Table 7-2](#) lists all laboratory assessments. All data obtained from these assessments must be supported in the patient’s source documentation. The table indicates which data are entered into the database (D) or may remain in source documents only (S) (column category). Assessments that generate data for the EDC system are listed.

Since dovitinib is given in a 5 days on/2 days off dosing schedule, day 12 assessments are intended to be performed on the last dosing day of the 2nd week in cycle 1 and cycle 2 and day 26 assessments are intended to be performed on the last dosing day of the 4th week in cycle 1 and cycle 2.

All assessments have a ±3 days window unless otherwise indicated. In the event of public holidays (e.g. Christmas, New Year’s Day), there is a ±5 days window on all assessments. Every effort must be made to follow the schedule of assessments within the windows outlined in the protocol. Additional assessment may be performed as clinically indicated.

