**Table 7-2 Laboratory assessment schedule**

	Test name	Category	Reference to assessment types	Baseline	Cycle 1		Cycle 2		Subsequent cycles	End of study treatment
Visit no.				1	2	3	4	5	6	7+
Day of cycle				-14 to -1	1	12	26	12	26	26
Hematology	Hemoglobin	D	7.10.11	X	X	X	X	X	X	X
	RBC	D	7.10.11	X	X	X	X	X	X	X
	WBC	D	7.10.11	X	X	X	X	X	X	X
	Platelets	D	7.10.11	X	X	X	X	X	X	X
	Differentials:		7.10.11	X	X	X	X	X	X	X
	ANC	D								
	lymphocytes	S								
	monocyte	S								
	eosinophil	S								
	basophil	S								
Chemistry	Urea/BUN	S	7.10.11	X	X	X	X	X	X	X
	Creatinine	D	7.10.11	X	X	X	X	X	X	X
	Total bilirubin	D	7.10.11	X	X	X	X	X	X	X
	ALT	D	7.10.11	X	X	X	X	X	X	X
	AST	D	7.10.11	X	X	X	X	X	X	X
	GGT	D	7.10.11	X	X	X	X	X	X	X
	Alkaline phosphatase	S	7.10.11	X	X	X	X	X	X	X
	Albumin	D	7.10.11	X	X	X	X	X	X	X
	Total protein	S	7.10.11	X	X	X	X	X	X	X
	Calcium	D	7.10.11	X	X	X	X	X	X	X
	Sodium	S	7.10.11	X	X	X	X	X	X	X
	Magnesium	D	7.10.11	X	X	X	X	X	X	X
	Potassium	D	7.10.11	X	X	X	X	X	X	X
	Phosphorous	D	7.10.11	X	X	X	X	X	X	X
	Glucose	S	7.10.11	X	X	X	X	X	X	X
	LDH	D	7.10.11	X	X	X	X	X	X	X
	Amylase	D	7.10.11	X	X	X	X	X	X	X
	Lipase	D	7.10.11	X	X	X	X	X	X	X
Serum lipid profile	Total cholesterol, triglycerides, LDL, HDL	S	7.10.11	X			X		X	X
Coagulation	PT or INR	S	7.10.11	X				X	X a	
	PTT	S	7.10.11	X				X	X a	
	Fibrinogen	S	7.10.11	X				X	X a	

Urinalysis	Dipstick: specific gravity, PH, protein, blood, glucose...	S	7.10.11	X f			X b		X b	X b	
	Microscopic: WBC, RBC, bacteria, casts...	S	7.10.11	X			X b		X b	X b	
Thyroid function	TSH, T3, T4	D	7.10.11	X					X c		X
Cardiac enzymes	CPK, CK-MB, troponin T or I	S	7.10.11	X			X d		X d	X d	
Pregnancy e test		S	7.10.11	X			X		X	X	

aAdditional PT/INR, PTT, and Fibrinogen studies will be performed only as clinically indicated in subsequent treatment cycles.

bAdditional urine dipstick and microscopic studies will be performed only as clinically indicated in subsequent treatment cycles.

cAdditional TSH, T3, and T4 studies will be performed (+/- 5 days) on cycle 3 day 26, cycle 6 day 26 and as clinically indicated in subsequent treatment cycles.

dAdditional CPK, CK-MB, troponin T or I studies will be performed only as clinically indicated in subsequent treatment cycles.

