## **8 Safety Monitoring and Reporting**

### **8.1 Adverse Events**

#### **8.1.1 Definitions and Reporting**

An adverse event for the purposes of this protocol is defined as the appearance of (or worsening of any pre-existing) undesirable sign(s), symptom(s), or medical condition(s).

Abnormal laboratory values or test results constitute adverse events only if they induce clinical signs or symptoms, are considered clinically significant, or require therapy.

Adverse events will be assessed according to the Common Terminology Criteria for Adverse Events (CTCAE) version 4.0. If CTCAE grading does not exist for an adverse event, the severity of mild, moderate, severe, and life-threatening, or grades 1 - 4, will be used. CTCAE grade 5 (death) will not be used in this study; rather, this information will be collected and recorded in the Adverse Events eCRF as end of treatment or survival information.

Adverse events will be recorded from the time of consent and for at least 30 days after treatment discontinuation. All Adverse events considered related to trial medication will be followed until resolution, return to baseline, or deemed clinically insignificant, even if this occurs post-trial.

Abnormal laboratory values or test results occurring after signing the informed consent form constitute adverse events only if they induce clinical signs or symptoms, or require therapy, (e.g., any hematologic abnormality that requires transfusion or hematological stem cell support) or changes in study medication(s) are considered clinically significant and should be recorded on the Adverse Events eCRF under the signs, symptoms or diagnosis associated with them. In addition, isolated abnormal laboratory values that are considered clinically significant (e.g., cause study discontinuation or constitutes in and of itself a Serious Adverse Event) should be recorded on the Adverse Events eCRF.

The occurrence of adverse events should be sought by non-directive questioning of the patient (subject) during the screening process after signing informed consent and at each visit during the study. Adverse events also may be detected when they are volunteered by the patient (subject) during the screening process or between visits, or through physical examination, laboratory test, or other assessments. As far as possible, each adverse event should be evaluated to determine:

1. The severity grade (CTCAE grade 1-4)

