## **9.4 Database Management and Quality Control**

Data will be entered into the study database by investigator/study coordinator for EDC studies.

For studies using eCRFs, Hoosier Cancer Research Network personnel will review the data entered by investigational staff for completeness and accuracy. Detected discrepancies for which the resolution is obvious/self-evident will be corrected by Hoosier Cancer Research Network

Data Management personnel. Electronic data queries are stating the nature of the problem and requesting clarification will be created for all other discrepancies and missing values and sent to the investigational site via the EDC system. Designated investigator site staff are required to respond promptly to queries and to make any necessary changes to the data.

Medical history/current medical conditions and adverse events will be coded using the Medical dictionary for regulatory activities (MedDRA) terminology.

Samples and/or data will be processed centrally and the results will be sent electronically to Hoosier Cancer Research Network.

At the conclusion of the study, the occurrence of any protocol violations will be determined. After these actions have been completed and the database has been declared to be complete and accurate, it will be locked and made available for data analysis.

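### Section 10.6.3.3 promises graded laboratory tables for hematology, biochemistry and urinary tests, but Table 7-2 lets several of those tests, including all urinalysis, stay out of the database

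*Combined protocol and SAP*

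**What the plan says.** Four parts of the combined protocol and SAP bear on this point.

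- **Planned outputs (10.6.3.3).** For tests that CTCAE covers, "the study's biostatistical and reporting team will grade laboratory data accordingly". Grade 0 goes to every non-missing value that does not reach grade 1. The section continues: "The following summaries will be generated separately for hematology, biochemistry and urinary laboratory tests". The outputs are a frequency table of newly occurring on-treatment grades, shift tables from baseline to the worst on-treatment value, and a listing of all laboratory data. White-cell differentials are named as an example where the CTCAE limits may need adapting, so they are evidently meant to be graded.
- **What must be entered (7.1).** On the category column of the schedules: "The table indicates which data are entered into the database (D) or may remain in source documents only (S) (column category".
- **What the analysis uses (9.4).** Once "the database has been declared to be complete and accurate, it will be locked and made available for data analysis".
- **What is coded S (Table 7-2).** Lymphocytes, monocytes, eosinophils and basophils; urea, alkaline phosphatase, total protein, sodium and glucose; the row "Total cholesterol, triglycerides, LDL, HDL"; all three coagulation rows; both urinalysis rows; the cardiac enzyme row; and the pregnancy test.

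**The concern.** The analysis section and the data-collection schedule do not match. A table that assigns grade 0 to normal values and compares baseline with the worst on-treatment value needs every measured value in the analysis database. For the S-coded tests, the protocol does not require any of them to be there.

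Some of these tests matter in the protocol's own background. Section 1.2.2 names alkaline phosphatase among the most frequent biochemistry abnormalities. Its toxicity summary reports grade 3/4 triglyceride increases, "88 with grade 3 and 18 with grade 4", and grade 3/4 lymphopenia as an adverse event in 21.4% of patients in the Japanese phase I study. At stake is whether the trial can report systematic graded laboratory results for these tests, or only those abnormalities that happened to qualify as adverse events.

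**Working it through.** The plan gives no figure to reproduce. The check is a row count of Table 7-2 set against the outputs in 10.6.3.3.

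**Step 1. Count D and S rows in the three named families.**

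| Family | D rows | S rows | Total |
|---|---|---|---|
| Hematology (hemoglobin, RBC, WBC, platelets, five differentials) | 5 | 4 | 9 |
| Chemistry | 13 | 5 | 18 |
| Urinalysis (dipstick, microscopy) | 0 | 2 | 2 |
| **Sum** | **18** | **11** | **29** |

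Table 7-2 lists lipids under their own heading as one S row covering four analytes. If lipids are treated as biochemistry, the S count becomes 11 + 1 = 12 of 29 + 1 = 30.

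**Step 2. Match the rows to the outputs.** ANC is the only differential coded D. Of 18 chemistry analytes, 5 have no required entry. The urinary family has no D row, so the whole urinary set of outputs has no required input.

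**Step 3. See whether another route fills the gap.** Under 8.1.1, "Abnormal laboratory values or test results constitute adverse events only if they induce clinical signs or symptoms, are considered clinically significant, or require therapy". Sections 8.1.1 and 8.1.3.1 also bring in abnormalities that lead to a change in study medication. This route does capture some relevant results:

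- Footnote d of the table in 6.1.4 calls for treatment of grade 2 or higher hypercholesterolemia or hypertriglyceridemia, and treated abnormalities are recorded as adverse events.
- The same table interrupts dosing for clinically significant lymphopenia of grade 3 or higher, which also triggers an entry.

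It does not supply grade 0 values, baseline values or the worst on-treatment value for each patient. A shift table cannot be built from it.

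**Step 4. Alkaline phosphatase as an example.** Section 7.5 collects it at baseline from all patients. Footnote e in 6.1.4 puts it in the liver function set with albumin, ALT, AST, total bilirubin and GGT. Those five are all D; alkaline phosphatase alone is S. The table in 6.1.4 also says that isolated values of grade 3 or higher do not require interruption, so such a value need not generate an adverse event entry. Even with the baseline value in the database, the on-treatment half of the shift table has no required source.

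**Step 5. Look for an override.** Section 9.4 mentions central processing of samples or data with electronic return of results. It names no safety-laboratory transfer that would replace the S coding.

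**The case against.** Several counter-arguments have force.

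- **S is permissive.** Section 7.1 says such data may remain in source, not that they must. A reader might infer that the values never reach the database and the tables are impossible. The text does not say so; the accurate statement is that entry is not required. Optional entry is a weak remedy, though, because denominators would then depend on site habit.
- **The adverse event form catches the most prominent examples.** This stands in part, as Step 3 shows. The 21.4% lymphopenia figure is itself an adverse event rate, and the triglyceride counts come without a denominator in that paragraph.
- **A biased toxicity endpoint.** A reader might infer that toxicity rates are biased low. The documents do not support that. The secondary endpoint is treatment-related toxicity, and 10.6.3.2 summarizes adverse events by grade and relation to drug. The tables in 10.6.3.3 are separate and carry no causality assessment. One patient in 20 is 1/20 = 5 percentage points, but that describes the denominator and does not measure bias.
- **Coagulation and cardiac enzymes.** A reader might add these to the list. Section 10.6.3.3 names three families, and Table 7-2 gives these tests their own headings. Only a broad reading of the all-data listing would include them.
- **Urinalysis would be sparse anyway.** Section 7.10.11.5 schedules it at baseline and afterwards only as clinically indicated. That stands: recoding alone would not yield a systematic urinary shift table.

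Most laboratory tests that drive dose modification, such as ANC, platelets, creatinine, bilirubin, ALT and AST, are D. That limits the importance of the gap but does not close it.

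**Conclusion.** The mismatch holds for the S-coded rows of the three named families: 11 of 29 rows, or 12 of 30 with lipids. Followed as written, the plan leaves the graded frequency tables, shift tables and full listing without required input for those tests, and the urinary family has none at all. The consequence is incomplete laboratory safety tables. The primary endpoint is untouched, and distortion of the treatment-related toxicity rates is not demonstrated.

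This rests on two assumptions: that S-coded values are not entered routinely, and that no electronic laboratory transfer exists beyond what the protocol describes. Whether lipids belong to biochemistry is a matter of reading. The conclusion for lymphocytes, alkaline phosphatase, sodium, glucose and urinalysis does not depend on it. It is worth correcting, because the promised outputs and the required data should agree and the repair is cheap.

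**What to change.** 1. In Table 7-2, change at least lymphocytes, alkaline phosphatase, sodium, glucose, total cholesterol and triglycerides from S to D. The lipid row must be split for the last two. Hematology would then have 5 + 1 = 6 of 9 rows coded D, and chemistry 13 + 3 = 16 of 18.
2. For tests left as S, and for urinalysis, restrict 10.6.3.3 to the D-coded tests. Remove the urinary tables and the reference to all laboratory data, and state in the report that graded rates were not estimated for the excluded tests.
3. State whether the full listing is meant to include coagulation and cardiac enzymes. Recode them only if it is.

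The six recoded analytes are already measured on schedule (7.10.11.1 to 7.10.11.3), so no test or visit is added. The cost is six more eCRF analytes per scheduled laboratory visit (fewer where lipids are not drawn) in about 20 patients, with the added site data entry. It is best settled before data entry starts, since later correction means retrieving values from source at several sites.

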#### **10.6.3.4 Other Safety Data**

##### **ECG**

- shift table baseline to worst on-treatment result for overall assessments
- lists of ECG evaluations for all patients with at least one abnormality.

##### **Vital Signs**

- shift table baseline to worst on-treatment result
- table with descriptive statistics at baseline, one or several post-baseline time points and change from baseline to this/these post-baseline time points.

#### **10.7 Exploratory Objectives**

In addition to the study's primary and secondary objectives, key exploratory objectives include:

- To characterize concordance rates between UC patient detected tumor, urine, and circulating free plasma FGFR3 mutations.
- To characterize associations between pre-treatment germline (as assessed by PBMC extracted DNA) FGFR SNPs and post-treatment 6-month complete response rate and 1-year relapse free survival rate in patients treated with dovitinib.

- To characterize associations between pre-treatment germline (as assessed by PBMC extracted DNA) VEGFR SNPs and post-treatment 6-month complete response rate and 1-year relapse free survival rate in patients treated with dovitinib.
- To characterize VEGFR over-expression status within tumor tissue
- To characterize pre- and post-treatment bladder tumor FGFR and VEGFR pathway phosphorylation changes as assessed by bladder tumor tissue immunohistochemistry.
- To characterize post-treatment bladder tissue dovitinib concentrations.
- To characterize associations between post-treatment hypertension, 6-month complete response rate and 1-year relapse free survival rate in patients treated with dovitinib.

#### **10.7.1 Exploratory Objectives Statistical Hypothesis, Model, and Method of Analysis**

All exploratory objectives are hypothesis generating in nature. Pre- and post-treatment phosphorylation changes in FGFR and VEGFR pathways will be analyzed by paired t-tests. FGFR SNPs, VEGFR SNPs, post-treatment hypertension, and baseline clinical factors of interest (e.g. age, ECOG PS, Charlson Comorbidity Index, gender, T1 vs. CIS, number of prior intravesical therapies, etc.) will be analyzed by univariate logistic regression and Cox regression for significant associations with 6-month CR and 1-year RFS rates, respectively. No multivariate models will be adopted given the small sample size. Concordance rates between tumor, urine, and circulating free plasma FGFR3 mutations will be summarized by Goodman-Kruskal gamma. The post-treatment bladder tissue dovitinib concentrations will be summarized by mean, standard deviation, minimum, median, maximum, and boxplot. Transformations to normality will be considered when necessary.

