ELIGIBILITY	
Inclusion
 
 
1. Histologically confirmed non-muscle invasive urothelial carcinoma of the bladder (NMIBC) defined as Ta, T1, or Tis stage. Tumor staging must be confirmed by TURBT performed within 42 days prior to registration.
 
2. Presence of either an FGFR3 mutation or FGFR3 over-expression within bladder tumor tissue. FGFR3 mutations (see Table 1-2) in exons 7, 10, and 15 will be assessed by massively parallel sequencing analysis utilizing the Ion Torrent Personal Genome Machine (PGM) in the CLIA-certified Molecular Pathology and Translational Research Laboratory at the Dartmouth Hitchcock Medical Center. FGFR3 over-expression will be assessed by standard IHC analysis performed within the Indiana University Simon Cancer Center Immunohistochemistry (IHC) Core Lab.
 
 
NOTE: Patients will initially be allowed to enroll if their tumors demonstrate either an FGFR3 mutation or FGFR3 over-expression. However, a minimum of 10 FGFR3 mutation positive patients will be enrolled at study completion. If 10 patients with tumors that are FGFR3 over-expressors but FGFR3 mutation negative are accrued prior to enrolling 10 FGFR3 mutation positive patients, subsequent enrollment will be restricted to patients with tumors that are FGFR3 mutation positive.
 
 
3. Documented BCG-refractory disease defined as failure to achieve a tumor free state after at least 2 prior intravesical treatment courses, one of which must have been intravesical BCG therapy.
 
 
NOTE: There is no maximum limit on the number of prior BCG therapy courses. In addition, there is no maximum limit on the number of prior non-BCG intravesical therapy courses (i.e. gemcitabine, valrubicin, interferon, mitomycin C, etc.).
 
 
4. Medically unfit to undergo cystectomy or electively choosing to forego cystectomy
 
5. ECOG (WHO) performance status 0 or 1 or 2
 
6. Age <math>\geq</math> 18 years old
 
7. Patients must have the following laboratory values: 
 
• White blood cell count (WBC) <math>> 3.0</math> K/mm^3
 
• Absolute neutrophil count (ANC) <math>\geq 1.5</math> K/mm^3
 
• Platelets <math>\geq 100</math> K/mm^3
 
• Hemoglobin (Hgb) <math>\geq 9</math> g/dL
 
• Serum total bilirubin: <math>\leq 1.5 \times</math> ULN
 
• ALT and AST <math>\leq 3.0 \times</math> ULN
 
• Serum creatinine <math>\leq 1.5 \times</math> ULN or serum creatinine <math>> 1.5 - 3 \times</math> ULN if calculated creatinine clearance (CrCl) is <math>\geq 30</math> mL/min using the Cockcroft-Gault equation, see formula below:
 
 
 
 
CrCl = <math>[140 - \text{age (years)}] \times \text{weight (kg)} / [72 \times \text{serum Cr (mg/dL)}]</math> (if patient is female multiply the above by 0.85)
 
 
• Urine dipstick reading: Negative for proteinuria or, if documentation of +1 (+2 for patients with renal cell carcinoma) results for protein on dipstick reading, then total
 

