#### **5.1 Inclusion Criteria**

Patients eligible for inclusion in this study have to **meet all** of the following criteria:

1. Histologically confirmed non-muscle invasive urothelial carcinoma of the bladder defined as Ta, T1, or Tis stage. Tumor staging must be confirmed by TURBT performed within 42 days prior to registration.
2. Presence of either an FGFR3 mutation or FGFR3 over-expression within bladder tumor tissue. Somatic FGFR3 mutations (see Table 1-2) in exons 7, 10, and 15 will be assessed in FFPE tumor tissues by massively parallel sequencing analysis utilizing the Ion Torrent Personal Genome Machine (PGM) and performed in the CLIA-certified Molecular Pathology and Translational Research Laboratory at the Dartmouth Hitchcock Medical Center. FGFR3 over-expression will be assessed by standard IHC analysis performed within the Indiana University Simon Cancer Center Immunohistochemistry (IHC) Core Lab.

NOTE: Patients will initially be allowed to enroll if their tumors demonstrate either an FGFR3 mutation or FGFR3 over-expression. However, a minimum of 10 FGFR3

mutation positive patients will be enrolled at study completion. If 10 patients with tumors that are FGFR3 over-expressors but FGFR3 mutation negative are accrued prior to enrolling 10 FGFR3 mutation positive patients, subsequent enrollment will be restricted to patients with tumors that are FGFR3 mutation positive.

3. Documented BCG-refractory disease defined as failure to achieve a tumor free state after at least 2 prior intravesical treatment courses, one of which must have been intravesical BCG therapy.

**NOTE:** There is no maximum limit on the number of prior BCG therapy courses. In addition, there is no maximum limit on the number of prior non-BCG intravesical therapy courses (i.e. gemcitabine, valrubicin, interferon, mitomycin C, etc.).

4. Medically unfit to undergo cystectomy or electively choosing to forego cystectomy

5. ECOG (WHO) performance status 0 or 1 or 2

6. Age  $\geq$  18 years old

7. Patients must have the following laboratory values:

- White blood cell count (WBC)  $\geq$  3.0 K/mm^3
- Absolute neutrophil count (ANC)  $\geq$  1.5 K/mm^3
- Platelets  $\geq$  100 K/mm^3
- Hemoglobin (Hgb)  $\geq$  9 g/dL
- Serum total bilirubin:  $\leq$  1.5 x ULN
- ALT and AST  $\leq$  3.0 x ULN

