- g. Archived pre-treatment tissue samples for study correlates will be collected from enrolled eligible patients. Blood and urine samples for study correlates will be collected at Cycle 1 Day 1 from enrolled eligible patients. The correlative analyses will be completed in batch groupings at study completion. Refer to SPM for collection, processing and shipping guidelines.
- h. Tissue for dovitinib PK analysis will be collected at the initial post-treatment cystoscopy with TURBT performed 3 months +/- 7 days after starting dovitinib therapy. Refer to SPM for collection, processing and shipping guidelines.
- i. Unstained slides are to be submitted from the pre-treatment TURBT specimen and from the post-treatment cystoscopy with TURBT performed 3 months +/- 7 days after starting dovitinib therapy. Refer to SPM for collection and shipping guidelines.

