#### **7.10.6.2 FGFR3 Overexpression Status**

Presence of FGFR3 over-expression within tumor tissue will be assessed at study entry by the IUSCC's IHC Core. The IHC antibody used to determine FGFR3 over-expression is commercially available from Novus Biologicals.

Refer to SPM for collection, labeling and shipping guidelines.

Presence of FGFR3 over-expression within tumor tissue will be assessed and interpreted by two separate pathologists. Brain, kidney, and testes are the recommended positive controls. Non specific immune serum will be used as the negative control. Staining intensity will be graded 0, +1, +2, +3 and  $\geq +1$  brown staining in the tissues defines positivity. Up to 3 pieces of tissue are to be analyzed at 3 to 5 high power fields if available.

Upon completion of testing, the presence/absence of FGFR3 over-expression will be communicated to the treating site within 5-7 days.

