#### **7.10.6.6 FGFR and VEGFR Pathway Signaling Analyses**

Assessment of the effect of dovitinib on FGFR and VEGFR pathway signaling will be assessed by the IUSCC IHC Core through analysis of pre- and post-treatment TURBT specimens.

All samples will be analyzed for FGFR3, pFGFR3, VEGFR2, pVEGFR2, FRS2, pFRS2, ERK, pERK by standard immunohistochemistry analysis with appropriate controls. Where additional tissue is available, analysis of additional FGFR/VEGFR pathway markers will also be performed. Refer to SPM for collection and shipping guidelines.

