#### **10.8 Sample Size Calculation**

The 6-month CR rate will be estimated with a one-sided 90% confidence interval of Agresti-Coull type with the lower bound to be calculated and the upper bound set as 1. With an expected CR rate of  $\geq 25\%$ , a sample size of 20 patients will have a power of 0.80 to exclude a lower bound being  $\leq 10\%$ .

Using a conservative estimate of FGFR3 mutation or over-expression present in 40% of BCG-refractory tumors, 50 patients will need to be screened in order to enroll the required 20 patients on dovitinib therapy.

The estimated accrual duration is 12 months and the estimated overall study duration is 2 years.

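### Patients who enter on FGFR3 over-expression alone are selected on the specimen that is also the paired t-test baseline, so their total FGFR3 staining should fall by regression to the mean even with no drug effect

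*Combined protocol and SAP*

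**What the plan says.** Section 10.7.1 states the method: "Pre- and post-treatment phosphorylation changes in FGFR and VEGFR pathways will be analyzed by paired t-tests". It gives no alpha, no control comparison, no adjustment for baseline and no split by entry route. It also says "All exploratory objectives are hypothesis generating in nature".

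Entry (Section 5.1) requires "Presence of either an FGFR3 mutation or FGFR3 over-expression within bladder tumor tissue". The accompanying note sets a quota: "a minimum of 10 FGFR3 mutation positive patients will be enrolled at study completion". Once 10 mutation-negative over-expressors have been accrued, enrollment is limited to mutation-positive patients until the minimum is met. For FGFR3 IHC (Section 7.10.6.2), intensity is graded 0 to +3, and +1 or more "brown staining in the tissues defines positivity". Section 7.2 takes this status from a TURBT within 42 days of registration.

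For the paired comparison, Table 7-1 footnote i says "Unstained slides are to be submitted from the pre-treatment TURBT specimen", with a second set from the 3-month TURBT. Section 7.10.6.6 gives the purpose as assessing dovitinib's effect on pathway signaling and lists the panel: "All samples will be analyzed for FGFR3, pFGFR3, VEGFR2, pVEGFR2, FRS2, pFRS2, ERK, pERK by standard immunohistochemistry analysis". The trial has one arm (Section 4.1.2).

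Section 1.2.3 announces that phosphorylation changes will be characterized by over-expression versus mutation status. Section 10.7.1 does not carry this forward.

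**The concern.** A paired t-test asks whether the mean change is zero. In a single-arm study that is the same as asking whether the drug did nothing only if the baseline value played no part in deciding who entered. Here it did for one group. A mutation-negative patient scoring 0 on the pre-treatment TURBT is screened out, while the 3-month score has no such filter. Some patients scored at least +1 partly because of sampling or reading variation, and on average they will score lower the second time.

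The result would be a fall in total FGFR3 that looks like a drug effect, with no control arm to expose it. A rank test or complete tissue at both visits would not remove it. A comparison by entry route without a caveat could also mislead, because the staining-selected group would show the larger fall from selection alone.

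**Working it through.** **Inputs from the documents**
- N = 20 (Section 10.8). At least 10 are mutation positive, so at most 20 − 10 = 10 enter on staining alone (50%).
- Share of mutation-negative tumors that over-express, from Table 1-1, where the mutation and over-expression rows add to the total row: Ta 13/(100 − 67) = 13/33 = 39%; T1 15/(100 − 42) = 15/58 = 26%.
- Share of eligible tumors that qualify on over-expression only, from the same table: Ta 13/80 = 16%, about 3 of 20; T1 15/57 = 26%, about 5 of 20.

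The plan has no figure of its own to reproduce for these tests. Its stated power of 0.80 concerns the primary endpoint and is not an input here.

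**Assumptions (not in the documents)**
- Two-sided alpha 0.05.
- Correlation rho between the two specimens' staining of 0.5 to 0.8.
- Normal latent staining, with the entry reading reused as the baseline.
- Mutation-positive tumors have the latent staining distribution of unselected tumors.
- Scores of 0 to 3 cut at the entry threshold, +0.6 SD and +1.2 SD.

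**Expected fall with no drug effect.** If the top share f is selected at cut z, the mean fall in SD units is (1 − rho) × φ(z)/f. The ratio φ(z)/f is 0.977 for f = 39% and 1.251 for f = 26%.
- rho 0.5: 0.5 × 0.977 = 0.49 SD (Ta) and 0.5 × 1.251 = 0.63 SD (T1).
- rho 0.8: 0.2 × 0.977 = 0.20 SD (Ta) and 0.2 × 1.251 = 0.25 SD (T1).
- Averaged over 20 patients of whom 10 are selected, these halve.

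**False rejection of the paired t-test on total FGFR3.** Simulated with no drug effect, N = 20. The 39% and 26% rows cover rho 0.8 to 0.5.

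| Staining-only + mutation-positive | Positivity f | 0–3 scores | Continuous |
|---|---|---|---|
| 10 + 10 (ceiling) | 39% | 12–21% | 10–18% |
| 10 + 10 (ceiling) | 26% | 17–32% | 13–25% |
| 3 + 17 (Table 1-1, Ta) | 39% | 5–6% | 5–6% |
| 5 + 15 (Table 1-1, T1) | 26% | 8–12% | 7–9% |
| 10 + 10 | 80% | 6–7% | 5–7% (rho 0.9 to 0.5) |

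At 10 + 10 on scores, at least 96% of the false rejections are falls. At rho 0.9 the ceiling figures on scores drop to about 9–12%. In the 10 staining-only patients alone the score test rejects 15–46% of the time. In mutation-positive patients alone it rejects about 5% on the continuous scale and 1–3% on scores.

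**pFGFR3.** This marker is affected only through its correlation with the FGFR3 entry reading. At an assumed correlation of 0.8 (continuous scale), rejection is 8–18% at 10 + 10, about 5–5.5% at 3 + 17 and 6–8% at 5 + 15. At rho 0.7, 10 + 10 and f = 39%, it is 5.1% with no correlation, 6.9% at correlation 0.5 and 8.7% at 0.7.

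**Re-staining.** Suppose the baseline is a fresh stain of the same block, assumed to correlate 0.9 with the entry reading. At 10 + 10 on the continuous scale, rejection is then 13/8/6% (Ta) and 18/10/7% (T1) at rho 0.5/0.7/0.8. The bias shrinks but remains.

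**The case against.** Several points against the concern carry weight.

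- **Half is a ceiling.** The quota caps staining-only entrants and does not predict them. At the mix that Table 1-1 itself implies, most of the inflation goes. This stands.
- **The sentence in 10.7.1 names phosphorylation, and entry is on total FGFR3.** This stands in part. Section 3.3.1 lists total FGFR3 among the markers for this endpoint, so it is within the planned comparison, but the effect on the phospho-markers is indirect and smaller.
- **The threshold is lenient.** If +1 captures most mutation-negative tumors, there is little selection. Section 10.8 plans on 40% of tumors having a mutation or over-expression; with mutation share m, positivity among mutation-negative tumors is then (0.4 − m)/(1 − m), at most 40%. That figure is described as conservative, so the true rate may be higher.
- **The entry reading may not be reused.** Table 7-1 footnotes f and i describe separate slide submissions. Re-staining reduces the bias without removing it.
- **The analysis is exploratory.** No decision or primary or secondary endpoint rests on it. This limits severity. However, a hypothesis-generating label does not excuse a predictable bias that goes unmentioned.

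A reader might infer that the paired t-tests reject falsely in up to a third of trials, or that false rejections of the phosphorylation tests would nearly always look like target inhibition. The documents do not support either. The first needs the quota ceiling, the T1 positivity rate and low repeatability together. The second fails because the plan does not define the phosphorylation variable: if a pFGFR3/FGFR3 ratio were used and FGFR3 fell more than pFGFR3, the ratio would rise.

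**Conclusion.** The mechanism follows from the documents: the same pre-treatment TURBT decides entry for over-expression-only patients and serves as their baseline, FGFR3 is in the panel, and there is no control arm. For total FGFR3 the bias is downward for any between-specimen correlation below 1.

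Its size is not fixed by the documents. Under the stated assumptions, false rejection on total FGFR3 scores is about 12% to 32% at 10 + 10, about 5% to 12% at the Table 1-1 mix, and 6% to 7% at 10 + 10 with 80% positivity. For pFGFR3 at correlation 0.8 it is about 8% to 18% and 5% to 8% in the first two settings. Alpha, repeatability, the FGFR3–pFGFR3 correlation and this assay's positivity rate are all assumed. Markers unrelated to FGFR3 staining are not affected. This is a low-severity improvement to an exploratory analysis.

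**What to change.** Carry the split announced in Section 1.2.3 into Section 10.7.1:

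- Report paired FGFR3 and pFGFR3 changes by entry route (mutation positive; over-expression only).
- Base the test of drug effect on the mutation-positive patients, who enter whatever their IHC score.
- Report over-expression-only patients descriptively, stating that their change includes regression to the mean from selection on baseline FGFR3 staining.
- Leave the markers not used for entry (VEGFR2, FRS2, ERK and their phospho-forms) pooled.
- Define the phosphorylation variable (pFGFR3 alone or relative to FGFR3), and say whether the entry reading or a fresh stain is the baseline.

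The cost is a few sentences, with no new samples or assays, since mutation and IHC status are already collected. The downside is precision: the FGFR3 and pFGFR3 tests would use fewer pairs. The quota guarantees at least 10 enrolled mutation-positive patients, not 10 usable pairs, so the tested set could be smaller than 10.
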